4.0 Treatment plan

4.1 Overview

This will be a phase II, non-randomized trial to determine the efficacy and safety of the combination of Eribulin, and lenvatinib in patients with metastatic breast cancer, non-small cell lung cancer and sarcoma. Treatments will be given in cycles of 3 weeks (21 days) and staging scans(CT Scans) will be performed every 2 cycles. Bone scans and MRI brain will be optional. Toxicity assessment will take place after each cycle.

Eribulin will be administered on cycle days 1 and 8; lenvatinib is an orally administered medication which will be given daily throughout each cycle (on cycle 1 lenvatinib will be started on day 2). On days when both drugs are administered, Eribulin will be administered immediately prior to lenvatinib.

Patients will be followed after treatment discontinuation until disease recurrence or death. An evaluable patient for toxicity is any patient who has received at least 1 dose of any of the study drugs. An evaluable patient for efficacy is any patient who has received at least 2 cycles of therapy.

There will be a safety run-in phase. Ten patients will receive lenvatinib at 20 mg daily and Eribulin at 1.4 mg/m² day 1 and day 8 of a 21 day cycle. Eribulin will be given on day 1 and lenvatinib at 20 mg daily will be started on day 2. After completion of 1 cycle of therapy for the first 10 patients the PI will have a teleconference with the medical team at EISAI and decide whether to continue at the same dose or increase the dose to 24 mg daily of lenvatinib and Eribulin at 1.4 mg/m² day 1 and day 8 of a 21 day cycle.

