4.7 Duration of Therapy

Patients may continue on study therapy until disease progression or until unacceptable toxicity occurs.

Patients will go off study therapy if any of the following occurs:

- The patient experiences any grade 4 toxicity after 2 dose modifications, as recommended by the protocol. If treatment is held for 2 consecutive treatment cycles due to toxicity, the patient must go off treatment.
- The patient withdraws consent from treatment or from the study as a whole.
- There is disease progression.
- The treating physician feels it is necessary (e.g. due to patient non-compliance or other safety concerns).

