5.3 Response Criteria

Response will be based on evaluation of target and non-target lesions. To be assigned a best response of partial response (PR) or complete response (CR), changes in tumor measurements must be confirmed by repeat studies that should be performed at a minimum of 4 weeks after the criteria for response are first met. A best response of SD will not require a confirmatory measurement; however, best overall response of SD will not be assessed unless a patient has received at least 2 complete cycles of treatment.

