5.3.3 Evaluation of Best Overall Response

The best overall response is the best response recorded from the start of the treatment until disease progression/recurrence (taking as reference for progressive disease the smallest measurements recorded since the treatment started). The patient's best response assignment will depend on the achievement of both measurement and confirmation criteria (see section 6.4).

Patients with a global deterioration of health status requiring discontinuation of treatment without objective evidence of disease progression at that time should be classified as having “symptomatic deterioration.” Every effort should be made to document the objective progression, even after discontinuation of treatment.

In some circumstances, it may be difficult to distinguish residual disease from normal tissue. When the evaluation of complete response depends on this determination, it is recommended that the residual lesion be investigated (fine needle aspirate/biopsy) before confirming the complete response status.

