5.3.4 Endpoint Assessment

The overall response rate (ORR) will be defined as response after scans assessed after two cycles of therapy (1 cycle = 3 weeks). Clinical response will be assessed by the treating physician as outlined above. All patients who are on study after 2 cycles will be considered evaluable for the response endpoints.

Progression-free survival (PFS) will be defined as the time from the first study treatment to the first occurrence of progression or death. All patients who receive at least one dose of each drug will be evaluable for this endpoint.

Toxicity will be assessed NCI CTCAE v 4.03. The incidence, nature, and severity of adverse events will be determined. All patients who receive at least one dose of study drug will be considered evaluable for toxicity and safety endpoints.

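### The primary response rate leaves out patients who stop before two cycles, and n=30 is not tied to treated or evaluable patients, so the same data can pass or fail

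*Combined protocol and SAP*

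**What the plan says.** Section 4.1 (Overview) sets the efficacy population: "An evaluable patient for efficacy is any patient who has received at least 2 cycles of therapy". Section 5.3.4 (Endpoint Assessment) words the condition differently for the primary endpoint: "All patients who are on study after 2 cycles will be considered evaluable for the response endpoints". The other endpoints use dose-based sets. Toxicity needs one dose of any study drug (4.1), and for progression-free survival 5.3.4 says: "All patients who receive at least one dose of each drug will be evaluable for this endpoint".

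For a response to count, section 5.3 requires that "changes in tumor measurements must be confirmed by repeat studies that should be performed at a minimum of 4 weeks" after the criteria are first met. Section 5.3.3 names a class for early clinical failure ("Patients with a global deterioration of health status requiring discontinuation of treatment without objective evidence of disease progression"), called symptomatic deterioration, but does not say whether these patients stay in the denominator of the response rate.

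Section 8.1.2 plans 30 patients at the MTD, with a poor rate of 0.20 and a good rate of 0.40. The regimen is judged promising if the one-sided 90% exact lower bound exceeds 0.20. The printed table gives rejection at 10 or more responders, actual alpha 0.0611 and power 0.8237. It does not say whether the 30 are treated or evaluable, or to which population 0.20 and 0.40 refer. Section 8.2 adds only descriptive statistics and confidence intervals. The plan states no replacement rule.

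**The concern.** Patients who leave in the first six weeks because of progression, toxicity, deterioration or death are treatment failures. If the denominator starts after two cycles, they vanish from the primary result, and the response rate and its interval describe a selected subset.

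The two wordings also select different patients. Section 4.7 separates leaving treatment from leaving the study ("The patient withdraws consent from treatment or from the study as a whole"). A patient who stops drug in cycle 1 but stays in follow-up may therefore count under 5.3.4 and not under 4.1. Section 6.0 schedules imaging every two cycles or at study termination, so an early progressor can be scanned and classed as progressive disease yet still fall outside the 4.1 set.

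Sections 5.3 and 5.3.3 do not repair this. The two-cycle minimum in 5.3 applies to stable disease only ("best overall response of SD will not be assessed unless a patient has received at least 2 complete cycles of treatment"), and 5.3.3 runs the best-response window from first treatment ("The best overall response is the best response recorded from the start of the treatment until disease progression/recurrence"). Neither is a denominator rule, but neither carries the exclusion made in 4.1.

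At stake is the decision on whether the combination merits further study. It depends on a denominator that could be chosen after the responses are known.

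**Working it through.** **Inputs.** From section 8.1.2: n=30, p0=0.20, p1=0.40, one-sided target alpha 0.10, cut-off R≥10. From 4.1 and 5.3: 21-day cycles, scans every two cycles, confirmation at least 4 weeks later. The documents give no early-exit rate for this trial, so d = 5, 10, 20 and 30% is an assumed range, with every early leaver a non-responder.

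**1. The plan's own figures reproduce.** P(X≥10 | 30, 0.20) = 0.0611 and P(X≥10 | 30, 0.40) = 0.8237. With R≥9 alpha would be 0.1287, so 10 is the right cut-off at n=30.

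**2. Timing.** The first scheduled scan comes after 2 × 21 = 42 days. Confirmation is due no earlier than 42 + 28 = day 70. On scheduled scans, a patient who dies or leaves the study within two cycles cannot have a confirmed response.

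**3. Verdict on the same responders.** The one-sided 90% exact lower bound L solves P(X≥x | n, L) = 0.10.

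| Responders | Denominator | Lower bound | Result |
|---|---|---|---|
| 9 | 30 | 0.190 | fail |
| 9 | 29 | 0.197 | fail |
| 9 | 28 | 0.204 | pass |
| 8 | 30 | 0.162 | fail |
| 8 | 24 | 0.205 | pass |
| 10 | 30 | 0.218 | pass |
| 10 | 33 | 0.198 | fail |

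Excluding one of 30 does not change the result for 9 responders; excluding two does. The last pair covers 33 treated to obtain 30 evaluable. The smallest r with P(X≥r | n, 0.20) ≤ 0.10 is 8 for n=21–24, 9 for n=25–28 and 10 for n=29–32. The printed cut-off and the bound rule therefore agree only for n=29–32.

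**4. Operating characteristics.** Take m ~ Bin(30, 1−d) evaluable patients and R ~ Bin(m, p/(1−d)) responders, where p is the all-treated rate. The cut-off c(m) comes from the exact bound. Row C instead takes R ~ Bin(m, 0.20). Verdicts differ when c(m) ≤ R < 10.

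| Quantity | d=5% | 10% | 20% | 30% |
|---|---|---|---|---|
| Evaluable rate if all-treated rate is 0.20: 0.20/(1−d) | 0.211 | 0.222 | 0.250 | 0.286 |
| A. Type I error, 0.20 all-treated, bound on evaluable subset of 30 | 8.7% | 11.8% | 18.7% | 28.6% |
| B. Type I error, 0.20 all-treated, leavers replaced to 30 evaluable: P(Bin(30, 0.20/(1−d))≥10) | 8.2% | 11.0% | 19.7% | 34.5% |
| C. Type I error, 0.20 an evaluable rate, bound on subset | 6.6% | 6.9% | 6.6% | 6.4% |
| D. Type I error, 0.20 all-treated, 30 treated, R≥10 fixed | 6.1% | 6.1% | 6.1% | 6.1% |
| Verdicts differ, true all-treated rate 0.20 | 2.6% | 5.7% | 12.6% | 22.5% |
| Verdicts differ, true rate 0.30 | 7.1% | 14.2% | 26.2% | 37.7% |
| Verdicts differ, true rate 0.40 | 4% | 8% | 13% | 16% |

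Row A reaches 10% at d of about 7% (0.07 × 30 ≈ 2 patients), and row B at about 8.5%.

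**5. A rough gauge of d.** Section 2.2 reports a median treatment duration of 112 days for lenvatinib alone in endometrial cancer. Assuming a constant stopping rate, 1 − 0.5^(42/112) = 23% would stop by day 42. That is a different population and regimen, so it shows only that the range is not extreme.

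**The case against.** The strongest reply is that section 8.1.2 prints a fixed rule for 30 patients at the MTD, which can be read as 30 treated. On that reading 8 or 9 responders fail whatever the denominator, alpha stays at 0.0611 and only the reported estimate is affected. This is correct, and it limits the type I error claim. It does not settle the matter, because the same section states the rule first as an exact bound, sections 4.1 and 5.3.4 define an evaluable set for response, and nothing says which applies when fewer than 30 are evaluable.

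The exit rates are assumed, and the bias is zero if nobody leaves early. Eligibility requires a life expectancy above 12 weeks (3.1), which limits early deaths but not exits for toxicity, progression or withdrawal. If being on study in 5.3.4 includes follow-up, which runs until death under 4.8, only early deaths and full withdrawals drop out, and the 20–30% figures then rest on the 4.1 wording alone. Disagreement between denominators is also smaller at the design alternative of 0.40 than at 0.30. These points stand as limits on size.

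It can also be said that 5.3.4 defines the response rate by the scans after two cycles and does not mention confirmation. However, 5.3.4 refers back to the preceding response rules, and those include the confirmation requirement in 5.3.

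A restriction to evaluable patients can be a deliberate choice in an exploratory single-arm study. It would then need one definition, null and target rates stated for that population, and an account of how early failures are reported. The plan has none of these.

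**Conclusion.** The concern holds and should be corrected before the response data are analysed. As a measure of all treated patients, the planned response rate is biased upward whenever anyone leaves before two cycles: a true 0.20 becomes an expected 0.222 at 10% exit and 0.250 at 20%. With two early leavers among 30, nine responders can be reported as a pass or a fail.

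Type I error exceeds the 10% target only if 0.20 is an all-treated rate and either the bound is applied to the evaluable subset (above about 7% exit) or leavers are replaced (above about 8.5%). If 0.20 is an evaluable-patient rate, or if 30 are treated and R≥10 is fixed, type I error stays within the target and the fault lies in the estimate. The plan does not say which case applies. The power calculation itself is correct.

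**What to change.** By a dated amendment before response analysis, align sections 4.1, 5.3.4 and 8.1.2:

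- Define the primary response population as all patients who received at least one dose of study drug at the phase II dose. Count anyone without a documented confirmed response under 5.3 as a non-responder.
- State that n=30, R≥10, p0=0.20 and p1=0.40 all refer to that set. Alpha 0.0611 and power 0.8237 are then exact at every early-exit rate.
- If the final n lies outside 29–32, take the cut-off from the one-sided 90% exact bound, for example 9 at n=28 or 12 at n=40.
- State whether the ten run-in patients belong. The synopsis lists 10 and 30 separately, while the note under the lenvatinib dose table in 4.3 calls them the first ten of phase 2.
- Lenvatinib starts on day 2, so a patient given only day-1 eribulin is in this set but outside the progression-free survival set. Use one set for both endpoints or state the difference.
- Keep the two-cycle set, with a single definition, as a supportive analysis.

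If 0.20 and 0.40 are all-treated rates, this needs no extra patients or procedures; the reported response rate may be somewhat lower. If 0.40 was meant as a rate among evaluable patients, requiring 10 responders among 30 treated cuts power, P(Bin(30, 0.40(1−d))≥10), to 76, 68, 51 and 32% at 5, 10, 20 and 30% exit. Keeping 80% power would then need more patients (32 treated at 5% exit, 36 at 10%), so the population for both rates must be stated. Enrolling extra patients to reach 30 evaluable (30/0.90, so 34 at 10% exit) does not remove the bias unless early leavers are still counted.

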4.2 Study Drug Administration

Eribulin

Eribulin will be administered intravenously (IV) on days 1 and 8 of each cycle at a dose of 1.4 mg/m² over a 2-5 minute time period; on cycle day 1 in the Phase II portion of the trial; this will be immediately prior to Lenvatinib administration. Eribulin will be administered to the patient in the clinic (for drug preparation instructions, see section 7.0). Each cycle will last 21 (+/- 3) days. Laboratory tests will be performed within 2 days prior to days 1 and 8 of all cycles to assess toxicity and confirm that it is safe to proceed with treatment (see Section 7.0 for a complete listing of assessments). The dose of Eribulin will be calculated based on the BSA at study entry and *should only be recalculated if there is >10% change in body weight from baseline*. The actual body weight will be used for these calculations.

Lenvatinib

Lenvatinib will be self-administered by patients orally once a day during the study period. Patients will self-administer lenvatinib at home, except on study visit days. On these visit days, patients should take lenvatinib after chemotherapy is administered. Patients will be instructed to take each dose orally once daily, with or without food, starting on day 2 of cycle 1. The capsules should be swallowed whole without chewing, dissolving, or opening them. Patients should be instructed to take their dose of study drug at the same time each day. If the usual dosing time is missed, the patient should take the dose that day as soon as they remember as long as this is within 12 hours of the usual time the patient takes the dose. If it has been over 12 hours then this will be considered a missed dose. Patients should not make up missed or vomited doses; dosing should resume on the next calendar day unless otherwise instructed. Patients will be given a medication diary to record all doses taken, missed/skipped, or vomited. This diary will be reviewed with study personnel prior to dispensing medication for the next cycle.

4.3 Supportive Care Guidelines

Supportive therapy for neutropenia:

If grade 3 or 4 neutropenia develops (ANC<1000/uL), G-CSF (Neupogen) can be administered, at the discretion of the treating investigator, until resolution of neutropenia. Neulasta (PEG-filgrastim) 6mg SC for 1 dose is recommended. If Neulasta is given, chemotherapy cannot be administered within 14 days. Neupogen can also be given at the discretion of the treating investigator. NOTE: Neupogen can be given any time before or after chemo. HOWEVER, Neulasta cannot be given within 14 days of chemotherapy.

Supportive therapy for neuropathy

Gabapentin or similar medications can be given at the discretion of the treating physician per institutional practice.

Dose Delays & Dose Modifications

Toxicities will be graded using NCI CTCAE version 4.03 (see Appendices). Dose delays and modification of lenvatinib and Eribulin are summarized below (for post-DLT period in phase II patients only). Individual patient dose reductions are also provided in separate tables.

Dose Delay & Modification for Eribulin and Lenvatinib

Toxicity	Adverse event	Dose Reduction/Delay	
		Eribulin	Lenvatinib
Hematologic toxicity attributed to any or all treatment	Platelets 75000-99999/mm ³ within 24 hrs prior to scheduled therapy	If Day 1: Hold until recovery of platelets >100,000/mm ³ . Resume at the same level after recovery If Day 8: No intervention	No dose modification necessary
	ANC <1000/mm ³ or Platelets 25000-74999/mm ³ within 24 hrs prior to scheduled therapy	If Day 1: Hold until recovery to ANC >1000/mm ³ and Platelets 100000/mm ³ . Resume at same level after recovery If Day 8: Hold until recovery to ANC >1000/mm ³ and Platelets 75000/mm ³ . Resume at same level after recovery	Hold until recovery to ANC >500/mm ³ and platelets more than 25000, Resume at same level after recovery.
	Platelets <25000/mm ³ or Platelets 25000-50000/mm ³ complicated by bleeding, easy bruising, petechiae, or requiring platelet transfusion	If Day 1: Hold until recovery to Platelets 100000/mm ³ . Resume at same level after recovery If Day 8: Hold until recovery to Platelets 75000/mm ³ . Resume at same level after recovery	Hold until recovery of Platelets 25000/mm ³ . Resume at current dose level.

	Prolonged neutropenia (ANC<500/mm ³ for >7 days)	Hold until recovery to ANC>1000/mm ³ . Resume at one dose level below current dose level	Hold until recovery to ANC>500/mm ³ . Resume at same level dose.
	Febrile neutropenia (ANC <1000/mm ³ with temperature of >38.5°C)	Hold until recovery to ANC>1000/mm ³ . Resume at one dose level below current dose level	Hold until recovery to ANC>1000/mm ³ . Resume at same dose level
	Anemia	No reduction or delay	No reduction of delay
Hepatic toxicity	Grade 4 AST, ALT or Total Bilirubin Child Pugh Score	For patients with known liver dysfunction and Child Pugh score A, Eribulin should be started at a dose of 1.1mg/m ² . For patients with known liver dysfunction and Child Pugh score B, Eribulin should be started at a dose of 0.7mg/m ² . Eribulin should not be administered in patients with Child Pugh score C. If during treatment there is grade 3,4 liver toxicity then dose reduce by 1 dose level.	Hold until recovery to Grade 1 or baseline. Resume at reduced dose of 20 mg po daily if first occurrence, reduce to 14 mg po daily on second occurrence and 10 mg po daily on third occurrence.

Peripheral neuropathy	Grade 3 or 4	Hold until recover to \leq grade 2. Reduce dose by one dose level. If neuropathy fails to recover to grade 2 within 3 weeks, Eribulin should be discontinued.	No modifications necessary
Non-hematologic toxicity grade 3 or 4 attributed to any or all treatment (except for neuropathy)	Grade 3 or 4 nausea/vomiting despite optimal antiemetic treatment	Hold until nausea/vomiting have resolved to \leq grade 1. Resume at same dose level	Hold until nausea/vomiting have resolved to \leq grade 1. Resume at same dose.
	>Grade 2 stomatitis	Hold until stomatitis has resolved to \leq grade 1. Resume at one dose level below current dose level	Hold until recovery to \leq grade 1. Resume at the same dose level
Hypertension	Grade 3 Hypertension Or life threatening Hypertension	No dose modification necessary.	Withhold lenvatinib for Grade 3 hypertension that persists despite optimal antihypertensive therapy; resume at one dose level below current dose level. Discontinue for life threatening hypertension.
Cardiac dysfunction or Hemorrhage.	Grade 3 or Grade 4 events	No dose modification necessary	Withhold lenvatinib for development of Grade 3 event until improved to Grade 0 or 1 or baseline. Either resume at a reduced dose or discontinue lenvatinib depending on the severity and persistence of the adverse event.
Proteinuria	>2 gms or less than 2 gms	No dose modification necessary.	Withhold lenvatinib for \leq 2 grams of proteinuria/24 hours. Resume at next dose level below current dose level; 2) when proteinuria is >2 gm/24 hours. Discontinue lenvatinib for nephrotic syndrome.
QTc Prolongation	Grade 3 or greater	No dose modification necessary	Monitor and correct electrolyte abnormalities in all patients. Withhold lenvatinib for the development of Grade 3 or greater QT interval prolongation. Resume lenvatinib at a one dose level below previous dose level when QT prolongation resolves to Grade 0 or 1 or baseline.

Day 8 dose of Eribulin may be delayed for a maximum of 1 week. If toxicities do not improve enough after 1 week delay then omit day 8 dose of Eribulin. If day 8 of Eribulin is omitted two consecutive cycles Eribulin should be resumed at one dose below current dose level.

Eribulin Dose Modifications

Starting dose and dose modifications for unacceptable toxicity that is thought to be related to Eribulin are listed below. Dose adjustments are to be made according to the greatest degree of toxicity. The most common toxic effects of Eribulin are fatigue, neutropenia (including neutropenic fever), peripheral neuropathy, and alopecia.

Eribulin Dose Modifications, TABLE 1

0	1.4
-1	1.1
-2	0.7

NOTE: Patients requiring a third dose reduction should be taken off study unless in the opinion of the investigator and/or the DSMB there is reason to believe that the patient is still experiencing clinical benefit (in such cases the DSMB will issue written approval).

Lenvatinib Dose Modifications

Recommended Dose Modifications for Persistent and Intolerable Grade 2 or Grade 3 Adverse Reactions or Grade 4 Laboratory Abnormalities, TABLE 2

0	20
-1	14
Note: Based on toxicity data of 1st 10 patients in Phase 2, starting Lenvatinib dose was not increased to 24 mg daily	

Other Toxicities with Lenvatinib

In the SELECT trial, QT/QTc interval prolongation was reported in 9% of lenvatinib-treated patients and 2% of patients in the placebo group. The incidence of QT interval prolongation of Grade 3 or greater was 2% in lenvatinib-treated patients compared to no reports in the placebo group. In the same trial, events of gastrointestinal perforation or fistula were reported in 2% of lenvatinib-treated patients and 0.8% of patients in the placebo group. 9% of lenvatinib-treated patients experienced Grade 3 or greater hypocalcemia compared to 2% in the placebo group. In most cases hypocalcemia responded to replacement and dose interruption/dose reduction.

Across clinical studies in which 1108 patients received lenvatinib, there were 3 reported events of reversible posterior leukoencephalopathy syndrome (RPLS). It is recommended to confirm the diagnosis with MRI and hold Lenvatinib until the resolution of the RPLS.

Lenvatinib impairs exogenous thyroid suppression. In the SELECT trial, 88% of all patients had a baseline thyroid stimulating hormone (TSH) level less than or equal to 0.5 mU/L. In those patients with a normal TSH at baseline, elevation of TSH level above 0.5 mU/L was observed post-baseline in 57% of Lenvatinib-treated patients as compared with 14% of patients receiving placebo. It is recommended to monitor TSH levels monthly and adjust thyroid replacement medication as needed in patients with DTC.

GI perforation and fistula formation has been reported in 2 % of the patients compared to 0.8 % patients in the placebo group. It is recommended to discontinue Lenvatinib in patient who had life threatening perforation or fistula formation.

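### The Neulasta recommendation in Section 4.3 and its two 14-day bars do not fit the day 1/day 8 eribulin calendar; where the recommendation is followed before a day-8 dose, that dose is lost and no rule covers the case

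*Combined protocol and SAP*

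**What the plan says.** The supportive-care text in Section 4.3 opens with: "If grade 3 or 4 neutropenia develops (ANC<1000/uL), G-CSF (Neupogen) can be administered, at the discretion of the treating investigator, until resolution of neutropenia". It continues: "Neulasta (PEG-filgrastim) 6mg SC for 1 dose is recommended". Two timing sentences follow. The first runs forward from Neulasta: "If Neulasta is given, chemotherapy cannot be administered within 14 days". The second gives no direction, so on its face it covers the days before and the days after an eribulin dose: "HOWEVER, Neulasta cannot be given within 14 days of chemotherapy". Neupogen is treated differently: "NOTE: Neupogen can be given any time before or after chemo".

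Four other provisions meet these:

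- Section 4.1: "Eribulin will be administered on cycle days 1 and 8".
- Section 4.2 sets the cycle at 21 days with a 3-day window either side, and schedules counts in the 2 days before days 1 and 8.
- The row for ANC below 1000 in the Section 4.3 modification table holds eribulin until counts recover, then resumes it at the same level.
- Below that table: "Day 8 dose of Eribulin may be delayed for a maximum of 1 week". If toxicity has not improved enough by then, the day-8 dose is omitted. Omission in two consecutive cycles lowers the eribulin dose level.

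For day 1, Section 4.3 gives no limit in days. Section 4.7 only takes a patient off treatment after two consecutive cycles held for toxicity.

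**The concern.** The one product that the text recommends carries a 14-day restriction in a regimen whose planned eribulin doses are 7 and 14 days apart. Depending on how the two timing sentences are read, the recommendation either cannot be followed at all or can cost an eribulin dose that the ANC row would otherwise permit. Sites in a multi-center trial would have to choose a reading for themselves. Neutropenia is a known toxicity of eribulin in the protocol's own background section, so the question will arise. What is at stake is eribulin exposure behind the response rate, and consistency between sites in how holds, omissions and reductions are applied.

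**Working it through.** The plan gives no figure to reproduce; the check is calendar arithmetic. Let s be the cycle day on which Neulasta is given.

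**Inputs.** Eribulin on days 1 and 8 (Section 4.1). Next day 1 = day 22, or day 25 at the end of the window (Section 4.2). Latest delayed day-8 dose = 8 + 7 = day 15 (Section 4.3). Bar = 14 days (Section 4.3).

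**1. Both timing sentences in force.** Neulasta needs s ≥ last dose + 14 and next dose ≥ s + 14, so next dose − last dose ≥ 28 days. The calendar offers:

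- day 1 to day 8: 8 − 1 = 7
- day 8 to next day 1: 22 − 8 = 14, or 25 − 8 = 17 with the window
- day 8 omitted: 22 − 1 = 21, or 25 − 1 = 24 with the window

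All are below 28, so no planned day qualifies. After a day-8 dose the first permitted s is 8 + 14 = 22, and the next eribulin is day 22 + 14 = 36, which is 14 days late.

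**2. Forward bar only, neutropenia found before the day-8 dose.** Earliest eribulin = s + 14. For s = 2 to 8 this is day 16 to 22, always past day 15. Suppose, for illustration, Neulasta on day 8 and ANC recovered on day 11. The ANC row says resume; the bar forbids eribulin until day 22; the one-week limit ended on day 15; and the omission rule is worded for toxicity that has not improved, whereas here it has. No rule applies. The cycle then delivers 1 of 2 planned doses (50%). Response is assessed after two cycles (Section 5.3.4), so this is 1 of the 4 planned doses before that scan.

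**3. Forward bar only, day-8 dose already given.**

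| Neulasta on day | Earliest next day 1 | Days late against day 22 | Within +3 window? |
|---|---|---|---|
| 8 | 22 | 0 | yes |
| 9 | 23 | 1 | yes |
| 10 | 24 | 2 | yes |
| 11 | 25 | 3 | yes |
| 12 | 26 | 4 | no |
| 15 | 29 | 7 | no |
| 22 | 36 | 14 | no |

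Days 8 to 11 fit. Later use delays day 1 but does not cancel it. For that cycle, day 15 means 21/28 = 75% of the planned eribulin rate, and day 22 means 21/35 = 60%.

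**4. If day 14 itself is barred,** replace 14 by 15. The required gap in step 1 becomes 30 days, step 2 gives days 17 to 23, and the usable days in step 3 shrink to 8 to 10 (10 + 15 = 25). The conclusions do not change.

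**5. When the trigger would be seen.** Scheduled counts fall on about days 6 to 8 and days 20 to 22. ANC below 1000 at the first check holds eribulin and leads to step 2. At the second, s + 14 = day 34 to 36, 12 to 14 days after day 22. Using days 8 to 11 after a given day-8 dose would normally need an unscheduled count.

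**The case against.** The strongest reply is that Neulasta is recommended, not required, and that the same paragraph offers Neupogen without a timing restriction. That stands. A site using Neupogen meets none of these conflicts. It limits the point but does not remove it: Section 4.6 asks that G-CSF follow the protocol's guidelines, and the only product those guidelines recommend is the one that does not fit.

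Several stronger readings are tempting and are not supported:

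- **Neulasta can never be given without disrupting the schedule.** On the forward bar alone, days 8 to 11 after a day-8 dose work.
- **Any slip of day 1 past the +3 window breaks the plan.** The one-week maximum covers the day-8 dose only. Day 1 is held until recovery with no cap in days, so late Neulasta produces a delay that the plan already tolerates.
- **The two readings of the bar add up.** Under the two-way reading Neulasta is unusable, and a site that turns to Neupogen loses no extra eribulin. The lost dose belongs to the forward-only reading.
- **Resuming at the same level contradicts the two-omission reduction.** One governs a hold followed by recovery, the other repeated omission; they can coexist. Only the counting of a dose withheld because of the bar is unclear.
- **The cited neutropenia rates (45.2%, 54% and 64%) measure the loss.** They are per-patient, single-agent rates of neutropenia, not of Neulasta use or of neutropenia on a dosing day. One of the cited phase II studies reports growth-factor use in 19% of patients in the first cycle, which does not give the frequency here either.

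It is also fair that ANC below 1000 already holds eribulin. The bar costs a day-8 dose only where counts would have recovered by day 15, and lengthens a day-1 hold only where recovery comes before the bar ends.

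**Conclusion.** The conflict is real and narrow. Read together, the two Neulasta sentences require 28 dose-free days, and the calendar offers no more than 17, or 24 with day 8 omitted. On the forward bar alone, Neulasta on days 2 to 8 before the day-8 dose makes that dose impossible by day 15, even after recovery, and the omission rule does not address the case. The cost is one of two planned eribulin doses in an affected cycle.

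This assumes that the site takes up the recommendation and, for the lost dose, that counts would have recovered in time. Section 4.3 introduces its modification table as applying to the post-DLT period in phase II patients. If the day-8 rule shares that scope, the clash with the one-week limit is documented for those cycles, while the clash between the two Neulasta sentences and the dosing days holds in any cycle.

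A reader might infer a measurable fall in response rate or power. The documents give no rate of Neulasta use and no relation between eribulin exposure and response, so neither can be calculated. The point should be fixed for consistent conduct; it does not undermine the design.

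**What to change.** The sponsor should reconcile the Neulasta recommendation and its two 14-day sentences in Section 4.3 with:

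- the dosing days and cycle window in Sections 4.1 and 4.2;
- the ANC hold-and-resume row of the Section 4.3 table;
- the day-8 delay and omission rule that follows the table.

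The text should say whether the second 14-day sentence runs in both directions and whether day 14 itself is included. It should also state whether an eribulin dose withheld only because of the 14-day bar counts toward the two-consecutive-omission dose reduction in Section 4.3 and toward the two-cycle hold rule in Section 4.7.

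Which provision should give way is a clinical decision for the sponsor, and none is proposed here. The cost is a wording amendment to Section 4.3 with a cross-reference in Section 4.7; sample size, endpoints and analysis are unaffected.
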